8.7.3 Antibody formation (secondary safety endpoint 2)

Serum samples will be tested for the presence of antibodies to botulinum toxin using an Anti Drug Antibody assay; initially only the last sample obtained from each study subject will be analyzed together with the pre-dose baseline sample. If a sample tests positive for anti-drug antibodies, the other samples from the subject will be analyzed to determine when antibodies developed. Serum samples which test positive for binding antibodies will subsequently be tested for neutralizing activity. Blood serum for ADA tests will be collected at screening, at the visit 4 weeks after treatment and at the end of cycle visit for each treatment cycle.

The presence of antibodies will be summarized by counts and percentages of subjects by treatment group and time point. For the subgroup of subjects with a sample test positive for anti-drug antibodies, all analyzed samples will be analyzed descriptively by counts over time as well.

8.7.4 Laboratory data (secondary safety endpoint 3)

For the purposes of summarization in both the tables and listings, all laboratory values will be presented in SI units. If a lab value is reported using a nonnumeric qualifier e.g., less than (<) a certain value, or greater than (>) a certain value, the given numeric value will be used in the summary statistics, ignoring the nonnumeric qualifier.

Visit value and change and/or percent change from baseline (where applicable) during the treatment period will be summarized by treatment group using descriptive statistics for all laboratory parameters.

All laboratory values will be classified as normal or abnormal according to the central laboratory normal ranges and indicated as clinically significant (CS) or not clinically significant (NCS) by the investigator. Quantitative laboratory values will be summarized with means, standard deviations, medians, minima and maxima at baseline and over time and of absolute changes from baseline. Categorical variables will be summarized by counts and percentages of subjects in corresponding categories. Shift tables illustrating changes with respect to the central laboratory normal ranges and the investigator assessment between baseline and post-baseline visits will be created: Number and percentage of subjects with normal, CS and NCS laboratory values.

8.7.5 Vital signs (secondary safety endpoint 3)

The analyses of variables for vital signs will focus on the evaluation of the change from baseline to the scheduled time points after baseline. Descriptive analysis with means,

standard deviations, medians, minima and maxima of the time course and of changes from baseline to each post-baseline visit by treatment cycle will be presented.

8.7.6 Electrocardiograms (secondary safety endpoint 3)

Normal/abnormal shift tables will be created for the overall ECG interpretation by treatment group for all applicable time points.

8.7.7 Physical examinations

All physical examination data and abnormalities will be listed only.

8.8 Other analysis

8.8.1 Subgroups

The following subgroup analyses will be performed for the primary efficacy endpoint. Subgroup analyses a) and b) will as well be conducted for all key secondary endpoints:

a) Subgroup analysis by geographic region, country, and site.

Subgroup analyses will be conducted for geographic region (US/EU), country, and site. Sites with less than three placebo subjects will be combined. The χ^2 -test will be applied for each subgroup. In case of a total number of observations below 30, or in case of at least one cell frequency below 5, Fisher's exact test will be used instead of the χ^2 -test. Stratified analyses applying the Cochran-Mantel-Haenszel test will also be conducted using factor geographic region and country. 95% CIs will be presented, if applicable. The modified Skindex-16 (GL-QoL) and FACE-Q Appraisal of Lines Between Eyebrows scale and FACE-Q Age Appraisal VAS scales will be analyzed by geographic region, country, and site according to the foreseen analysis approach of these tools, as described in section 8.6.3.

b) Subgroup analysis by subjects with previous use of botulinum toxin versus naïve subjects.

Subgroup analyses will be conducted for subjects with treatment with any serotype of botulinum toxin for any indication versus naïve subjects. The χ^2 -test or Fisher's exact test (see above corresponding criteria to use Fisher) will be applied for each subgroup. No stratified analysis using factor pre-treated/naïve subjects is currently planned. 95% CIs will be presented, if applicable. The modified Skindex-16 (GL-QoL) and FACE-Q Appraisal of Lines Between Eyebrows scale and FACE-Q Age Appraisal VAS scales will be analyzed by subjects with previous use of botulinum toxin versus naïve subjects according to the foreseen analysis approach of these tools, as described in section 8.6.3.

Statistical Analysis Plan (SAP)

c) Subgroup analysis by age groups.

Subgroup analyses will be conducted for subjects by age groups (below 65 years/ 65-74/ 75-84/ 85 years and older). The χ^2 -test or Fisher's exact test (see above corresponding criteria to use Fisher) will be applied for each subgroup. No stratified analysis using factor age is currently planned. 95% CIs will be presented, if applicable.

d) Subgroup analysis by gender.

Subgroup analyses will be conducted for subjects by gender (male/ female). The χ^2 -test or Fisher's exact test (see above corresponding criteria to use Fisher) will be applied for each subgroup. No stratified analysis using factor gender is currently planned. 95% CIs will be presented, if applicable.

e) Subgroup analysis by ethnicity.

Subgroup analyses will be conducted for subjects by ethnicity (Hispanic or Latino/ Not Hispanic or Latino). The χ^2 -test or Fisher's exact test (see above corresponding criteria to use Fisher) will be applied for each subgroup. No stratified analysis using factor ethnicity is currently planned. 95% CIs will be presented, if applicable.

f) Subgroup analysis by Fitzpatrick skin type.

Subgroup analyses will be conducted for subjects by Fitzpatrick skin type (Type I/ Type II/ Type III/ Type IV/ Type V/ Type VI). The χ^2 -test or Fisher's exact test (see above corresponding criteria to use Fisher) will be applied for each subgroup. No stratified analysis using factor Fitzpatrick skin type is currently planned. 95% CIs will be presented, if applicable.

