3.1 General study design

This multicenter Phase 3 study is comprised of two parts. The first part of the study is a randomized, double blind, placebo-controlled, phase which aims to demonstrate efficacy and safety of BoNT/A-DP compared with placebo. The second part is an open label extension phase to evaluate efficacy after repeat treatments and long term safety.

Subjects can receive a maximum of four treatment cycles over the duration of the study, a single treatment in the first cycle compared with placebo, and up to three subsequent treatments in the open label extension study.

Adult subjects less or equal 75 years old with moderate to severe glabellar frown lines at maximum frown with an important psychological impact as indicated by scores >0 on either the Emotional or Functioning subscales of the modified Skindex-16 (GL-QoL) will be enrolled in this study. Approximately 18 sites (50% in EU and 50% in US) will enroll in total 700 evaluable subjects. Applying a 10% drop out rate will result in a total number of completing subjects of about 630.

The overall study scheme is presented below:

[figure not shown]

The duration of study participation for each subject will be up to 14 calendar days of screening followed by 48 to 60 weeks of treatment (re-screening will not be permitted). The first treatment cycle will be a double blinded cycle followed by up to three open label treatment cycles. Each cycle will be at least 12 weeks and can be prolonged in 4-week increments, depending on treatment effect. Re-treatment is possible until study-week 48.

[figure not shown]
Statistical Analysis Plan (SAP)

Visit Scheme/Treatment Cycle 1 (double blind)

Visit Scheme/Treatment Cycles 2, 3, 4 (open label)

Statistical Analysis Plan (SAP)

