5 SAMPLE SIZE AND POWER

The primary endpoint is a composite endpoint comprising investigator and subject assessments of treatment effectiveness using the FWS. The FWS in this study corresponds to the FWS Investigator assessment (GLS-I) and the FWS for Subject self-assessment (GLS-S). Composite endpoint treatment success (CETS) is defined as ≥ 2 point reduction in FWS score at maximum frown achieving a score of 0 or 1 at the visit week 4 relative to baseline based on investigator assessment and subject assessment. Thus, a subject is a CETS “responder” only if both investigator- and subject-rated success criteria are satisfied at the visit 4 weeks after baseline.

The primary analysis of efficacy is the proportion of responders in the BoNT/A-DP treatment group compared with the placebo treatment group. For superiority testing of BoNT/A-DP compared with placebo, the following assumptions for the sample size calculation are used:

Statistical Analysis Plan (SAP)

Item	Assumption	Comments
Underlying test	Fisher's Exact Test	Standard test for a response parameter for small numbers
Randomization scheme	3:1	More active treatment subjects to enlarge safety data base
Power 1- β	90%	
Significance level (α)	0.025 one-sided	
Response Arm BoNT/A-DP	60%	From the range of observed response rates, a more conservative value of 60% has been chosen
Response Arm Placebo	10%	Conservative value
Software		The sample size calculation was performed using the software nQuery Advisor® 7.0.

Based on these assumptions, 42 subjects in the BoNT/A-DP arm and 14 subjects in the placebo arm are required, i.e. 56 subjects in total. This is a very small sample size and not sufficient for a detailed evaluation of the data, including subgroup analyses. Furthermore, the response rate could not be estimated with sufficient precision. A two-sided confidence interval (CI) of 95%, and a distance from the CI limit of about 4.5% could be achieved with a sample size of 450 subjects in the BoNT/A-DP group. Therefore, a 3:1 randomization of BoNT/A-DP (525 subjects) to placebo (175 subjects) was proposed, which should be adequate for a precise estimate of response rate and for post-hoc sensitivity analyses (i.e. treatment-by-center and other subgroup analyses), also taking into account a drop-out rate.

In total, 700 evaluable subjects will be enrolled. Applying a 10% drop out rate would result in a total number of about 630 subjects.

Statistical Analysis Plan (SAP)

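### Apart from Breslow-Day for site, the subgroup plan tests active against placebo within each level and specifies nothing that compares the treatment effect between levels

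*SAP*

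**What the plan says.** SAP 8.8.1 lists subgroup analyses of the primary endpoint by (a) region, country and site, (b) prior toxin use, (c) age, (d) gender, (e) ethnicity and (f) Fitzpatrick skin type. Factors (a) and (b) are repeated for the key secondary endpoints. Protocol 12.4.1 has the same method for (a) and (b).

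- **Test.** In each level, active is compared with placebo by chi-square. Fisher's test replaces it when the level has fewer than 30 observations or any cell is below 5. For factors (b) to (f) the wording is "see above corresponding criteria to use Fisher) will be applied for each subgroup".
- **Stratified analysis.** A Cochran-Mantel-Haenszel test is added for region and country. For the other five factors the SAP says no stratified analysis is planned.
- **Heterogeneity.** SAP 8.6.1.2 and Protocol 12.4.1 plan a Breslow-Day test of equal odds ratios across centers on the primary endpoint. No other interaction test is named.
- **Intervals.** SAP 8.8.1 promises 95% CIs where applicable without naming the quantity. Where responder CIs are defined (SAP 8.6.2, Protocol 12.4.1), they are Wilson intervals for each arm's responder rate.
- **Status.** SAP 8.6.1.1 makes everything outside the testing hierarchy exploratory.
- **Purpose of the sample size.** SAP 5 finds that 56 subjects suffice for the primary test. It justifies the larger trial ("a 3:1 randomization of BoNT/A-DP (525 subjects) to placebo (175 subjects) was proposed") by precision, by treatment-by-center and other subgroup analyses, and by dropout.

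**The concern.** A subgroup analysis is usually meant to show whether the effect is similar across kinds of patient. A test inside one level asks only whether there is any effect there. With an assumed effect as large as 60% v 10%, the answer depends mainly on how many subjects the level holds. A large level will be significant even if its effect is much reduced, and a small level may be non-significant with the full effect.

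The stratified CMH for region and country does not help, because it tests for an association common to the strata and does not compare effects between them. Per-arm intervals describe responder rates, not the treatment difference. Subgroup analysis is one stated reason for enrolling 700 subjects, yet outside site no specified analysis uses the trial's ability to compare effects.

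**Working it through.** **Inputs.** From SAP 5: alpha "0.025 one-sided"; active response 60% ("a more conservative value of 60% has been chosen"); placebo response 10%; 525 active and 175 placebo subjects. From SAP 3.1: "Approximately 18 sites (50% in EU and 50% in US) will enroll in total 700 evaluable subjects", so 700/18 = 38.9 per site, about 29:10 at 3:1. All other level sizes and splits below are assumptions, because the documents give none.

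**1. The plan's own figures.** Exact power of the one-sided Fisher test is the sum, over all outcomes with p ≤ 0.025, of the product of the two binomial probabilities. It is 89.3% at 39:13 and 91.6% at 42:14, which reproduces 42 + 14 = 56. The CI half-width at n = 450 is 1.96 × √(0.6 × 0.4/450) = 4.53%, which matches the stated value of about 4.5%.

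**2. Small levels with the full 60% v 10% effect.** Same Fisher calculation:

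| Active:placebo | Power | Non-significant |
|---|---|---|
| 6:2 | 0% | 100% |
| 9:3 | 5% | 95% |
| 12:4 | 15% | 85% |
| 15:5 | 24.7% | 75% |
| 18:6 | 43% | 57% |
| 24:8 | 61% | 39% |
| 29:10 (average site) | 75.5% | 24.5% |
| 36:12 | 86% | 14% |
| 42:14 | 91.6% | 8% |

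Across 18 sites of 29:10 with identical effects, the expected number non-significant is 18 × 0.245 = 4.4. The chance that all 18 are significant is 0.755^18 = 0.6%.

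**3. Large levels with a reduced effect.** Take a factor split 50/50 (262.5:87.5 per level, placebo 10%). A level with 40% response is significant with probability above 99.9%, and a level with 30% response with probability 98.7%. Halves with true rates 60% v 10% and 40% v 10% therefore both come out significant essentially always.

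**4. What an interaction test would see in step 3 (60% and 40% halves).**

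- Risk-difference scale: SE = √(2 × 0.24/262.5 + 2 × 0.09/87.5) = 0.0623. Then z = 0.20/0.0623 = 3.21, and power at two-sided 5% is Φ(3.21 − 1.96) = 89%.
- Log-odds-ratio scale: the difference is ln(1.5) − ln(0.667) = 0.811. SE = √(2/(262.5 × 0.24) + 2/(87.5 × 0.09)) = 0.535. Then z = 1.52, and power is 33%.

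As a second example, assume prior toxin users are 30% of subjects with 35% v 10%, against 60% v 10% in naive subjects. By simulation, both levels are significant in 97% of trials. Interaction power is 97% on the risk-difference scale and 46% on the odds-ratio scale.

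The gap in risk differences detectable with 80% power is (1.96 + 0.84) × SE, with 60% v 10% variances. It is about 17 points for a 50/50 split, 20 for 25/75 and 29 for 10/90.

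**5. Does a simple interaction test behave in sparse levels?** With equal effects (60% v 10%) and one small level against the rest, a Wald risk-difference test at nominal 5% rejects in about 11% of trials at 15:5, 13% at 9:3 and 21% at 6:2. An inverse-variance heterogeneity test over 18 sites of 29:10 rejects in about 16 to 17%. One reason is that 0.9^10 = 35% of sites are expected to have no placebo responder.

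**The case against.** A reader might infer that the plan never tests whether the effect differs. The documents do not support that, because Breslow-Day is planned for site on the primary endpoint. The 4.4 of 18 sites in step 2 therefore concerns the one factor that already has a homogeneity test, although a sparse one: about one placebo responder is expected per site (10 × 0.10).

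A reader might also infer that the plan will declare real differences consistent and small subgroups failures. Neither document says how a within-level p-value is to be read, and both treat these analyses as exploratory. The risk is one of misreading.

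The planned Wilson intervals do show something. With 60% and 40% active response in 262 subjects each, they are about 54–66% and 34–46% and do not overlap. But they compare active-arm rates. If placebo response also varies by level, they do not describe the effect, and no interval for the difference is specified.

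The most substantial objection concerns the remedy. Interaction power is high only on the risk-difference scale, whereas the plan's own homogeneity test uses odds ratios. The scale can even decide whether heterogeneity exists. With a common odds ratio of 13.5 and placebo rates of 10% and 5%, a risk-difference test rejects in 64% of trials and an odds-ratio test in 3%. A Wald risk-difference test also over-rejects in sparse levels (step 5). Both points stand and shape the fix, but neither closes the gap.

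**Conclusion.** The point holds in limited form. For region, country, prior toxin use, age, gender, ethnicity and skin type, no specified test or estimate compares the treatment effect between levels. The planned p-values mostly track level size: about 75% non-significant at 15:5 with the full effect, against near-certain significance in both halves when one has 40% instead of 60% response.

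The small-level problem applies below about 56 subjects, where power for the full effect falls under 90%. The age bands give a concrete case. With entry capped at 75 years, the 75–84 band can hold little beyond 75-year-olds and the oldest band should be empty, yet each is assigned its own test.

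No confirmatory conclusion or error rate is affected. The figures rest on the plan's 60% and 10% rates and 3:1 allocation. The 50/50, 25/75 and 10/90 splits, the 30% prior-use share and every level size except the average site are assumptions. This is worth correcting because it is cheap, and because the interaction scale would otherwise be chosen after the results are seen.

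**What to change.** In SAP 8.8.1, before unblinding:

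1. For each factor, report the risk difference with a Newcombe 95% CI at every level, in a forest plot.
2. Label within-level p-values descriptive, and say that they are not evidence of consistency or of failure.
3. Add one exploratory treatment-by-subgroup interaction test per factor, with its scale stated in advance.
4. Keep Breslow-Day for site. Pool sparse levels (for example skin types V–VI, and age 65 and over) or use a method valid in small samples. Do not apply a Wald risk-difference interaction test to levels of 20 or fewer subjects.
5. Do the same for key secondary endpoints 1–4 for factors (a) and (b).

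The cost is SAP wording and table and figure shells. No new data are needed, and the primary analysis and testing hierarchy do not change. There are two drawbacks. If the odds-ratio scale is chosen, interaction power is low (33% and 46% in the two examples), so a non-significant interaction is weak evidence of consistency. Small levels will show wide intervals.

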8.9 Interim analysis

Not applicable.

9 CHANGES TO PLANNED ANALYSIS FROM STUDY PROTOCOL

The following changes to the planned analysis from the study protocol are designated:

- The definition of the SAF in section 6 was changed compared to the definition in section 12.2 of the study protocol in order to include all treated subjects in the safety analyses.
- The analysis of antibody formation described in section 8.7.3 was changed compared to the description in the study protocol.

Statistical Analysis Plan (SAP)

